11.9.14.3.5. Study Drug Action Taken

The Investigator must classify the study drug action taken with regard to the AE. The action taken must be classified according to the categories shown in Table 16.

Table 16:Classification for Study Drug Action Taken With Regard to an Adverse
Event

Classification	Definition	
Dose Not Changed	Study drug dose not changed in response to an AE.	
Dose Reduced	Study drug dose reduced in response to an AE.	
Drug Interrupted	Study drug administration interrupted in response to an AE.	
Drug Withdrawn	Study drug administration permanently discontinued in response to an AE.	

Classification	Definition
Not Applicable	Action taken regarding study drug administration does not apply.
	"Not applicable" must be used in circumstances such as when the study drug had been completed before the AE began and no opportunity to decide whether to continue, interrupt, or withdraw study drug is possible.

Abbreviation: AE=adverse event

11.9.14.3.6. Adverse Event Outcome

All AEs will be followed until resolution, until deemed stable by the Investigator, or until the participant is deemed by the Investigator to be lost to follow-up or the participant completed the safety follow-up period. For the purposes of study analysis, if the event has not resolved at the end of the study reporting period, it must be documented as ongoing.

The outcome must be classified according to the categories shown in Table 17.

 Table 17:
 Adverse Event Outcome Definition

Classification	Definition	
Recovered/Resolved	Resolution of an AE with no residual signs or symptoms.	
Recovered/Resolved with Sequelae	Resolution of an AE with residual signs or symptoms.	
Recovering/Resolving	Improvement of an AE.	
Not Recovered/Not Resolved (Continuing)	Either incomplete improvement or no improvement of an AE, such that it remains ongoing.	
Fatal	Outcome of an AE is death. "Fatal" must be used when death is related to the AE.	
Unknown	Outcome of an AE is not known (eg, a participant lost to follow-up).	

Abbreviation: AE=adverse event

11.9.14.3.7. Treatment Given

The Investigator must ensure adequate medical care is provided to patients for any AEs. In addition, the Investigator must describe whether any treatment was given for the AE. "Yes" is used if any treatment was given in response to an AE and may include treatments such as other medications, hospitalization, surgery, or physical therapy. "No" indicates the absence of any kind of treatment for an AE.

11.9.14.3.8. Additional Points to Consider for Adverse Event

11.9.14.3.8.1. Clinically Significant Assessments

Study assessments including laboratory tests, ECGs, physical examinations, and vital signs must be assessed and those deemed as clinically significant must be documented as an AE. When possible, a clinical diagnosis for the study assessment must be provided rather than the abnormal test result alone (eg, urinary tract infection, anemia). In the absence of a diagnosis, the abnormal study assessment itself may be listed as the AE (eg, bacteria in urine or decreased hemoglobin). An abnormal study assessment is considered clinically significant if the patient has 1 or more of the following:

- Worsening, from baseline, concomitant signs or symptoms related to the abnormal study assessment
- Further diagnostic testing or medical/surgical intervention is required
- A change in the dose of study drug, if study drug is withheld, or discontinuation from study drug occurs

Repeat testing to determine whether the result is abnormal, in the absence of any of the above criteria, does not necessarily meet clinically significant criteria. The determination of whether the study assessment results are clinically significant must be made by the Investigator.

A laboratory abnormality judged to be Grade 4, in itself, may not constitute an SAE unless the clinical status of the patient indicates a life-threatening AE.

Symptoms of the disease under study must not be recorded as AEs as long as they are within the normal day-to-day fluctuation or expected progression of the disease, including significant worsening unless the deterioration was unexpected, and are part of the efficacy data to be collected in the study.

11.9.14.3.9. Monitoring and Recording Adverse Events

The AE (including SAEs) reporting period will begin after a participant signs the main ICF and will continue until completion of the Safety Follow-up Visit or 30 days after the final dose of study drug. Any SAE having an onset after the Safety Follow-up Visit will not be collected or reported unless the Investigator feels that the event may be related to the study drug. Only SAEs that are assessed by the Investigator as related to the biopsy will be collected after a participant signs the pre-screening consent and until the participant has signed the main ICF.

Participants will be instructed by the Investigator or designee to report the occurrence of any AE. All volunteered, elicited, and observed AEs are to be recorded.

If a participant begins a new TGCT therapy, the safety reporting period ends at the time the new treatment is started; however, death must always be reported when it occurs during the safety reporting period irrespective of intervening treatment.

The Investigator will assess all AEs regarding any causal relationship to the study drug, the intensity (severity) of the event, action taken, and participant outcome (see Section 11.9.14.3).

11.9.14.4. Reporting Adverse Events

11.9.14.4.1. Reporting of Serious Adverse Events

The written report for SAEs should be submitted on the SAE form provided for this purpose. The SAE report must include the Investigator's opinion as to whether the event is study drug related. If this relationship is determined to be related to study drug, evidence to support this assessment must also be provided.

For clinical study safety reporting purposes, the applicable version of the IB will be used as the reference document to designate event expectedness.

All SAEs that occur within the reporting period, regardless of causality, must be reported by the Investigator to Deciphera via the designee **immediately and no longer than 24 hours** from the point in time when the Investigator becomes aware of the SAE. Serious AEs must be followed until resolution, the condition stabilizes, or the Investigator and Sponsor agree that follow-up is not required. For purposes of regulatory safety monitoring, the Investigator is required to follow the event to resolution and report to the Sponsor the outcome of the event, unless the participant is deemed by the Investigator to be lost to follow-up or the participant completed the safety follow-up period.

If there are suspected unexpected serious adverse reactions (SUSARs) associated with the use of the study drug, the Sponsor or authorized designee will ensure that the appropriate regulatory agencies and all participating investigators are notified on an expedited basis. In addition, the Sponsor or authorized designee will be responsible for notification of SUSARs to the ethics committees. It is the responsibility of the Investigator to promptly notify the local IRB/IEC/ REB of SUSARs according to the institutional policy. An unexpected event is one that is not reported in the IB. Disease progression is not considered an AE. If AEs/SAEs occur in relation to disease progression that are not consistent with the nature and natural progression of the participant's disease, these AEs/SAEs must be reported per AE/SAE reporting requirements in this section.

11.9.14.4.2. Reporting of Pregnancy

The written report for pregnancies in female participants and in female partners of male participants should be submitted on the Pregnancy Report Form provided for this purpose within 24 hours of awareness of pregnancy.

Pregnancy is not considered an AE, although a female participant will be withdrawn from the study if a pregnancy occurs. Any pregnancy complication that meets the criteria of an SAE must be reported as per Section 11.9.14.4.1. The pregnancy, including a partner's pregnancy, must be reported to Deciphera or designee within 24 hours of site awareness, and additional follow-up may be required. In certain situations, reporting of partner pregnancies may not be necessary if mandated by local IRB/IEC/REB policy/investigative site Standard Operating Procedure.

If the female partner of a male participant becomes pregnant while on study, the male participant must notify the Investigator immediately, and the pregnant female partner should be advised to call her healthcare provider immediately. The male participant must commit to use acceptable methods of contraception (to ensure there is no exposure of the fetus to study drug) for the duration of the study and until 120 days following the last dose of study drug.

If the participant was receiving vimseltinib, the female participant or female partner of the male participant must be followed until the end of the pregnancy and the infant must be followed for 1 year after the birth, provided informed consent is obtained. A separate ICF will be provided to explain these follow-up activities.

11.9.14.4.3. Abuse, Misuse, Overdose, and Medication Error

Adverse events associated with drug abuse, misuse, overdose, or medication error must be reported as per Section 11.9.14.3.

Abuse of a medicinal product: Persistent or sporadic, intentional excessive use of medicinal products, which is accompanied by harmful physical or psychological effects [DIR 2001/83/EC Art 1(16)].

Misuse: Intentional and inappropriate use of a medicinal product not in accordance with the prescribed or authorized dose, route of administration, and/or the indication(s) or not within the legal status of its supply.

Overdose: Administration of a quantity of study drug given per administration or per day, which is above the assigned dose.

Medication Error: An error made in prescribing, dispensing, administration, and/or use of the study drug. Medication errors are reportable to the Sponsor as defined below.

- The dispensing, administration, and/or use of the unassigned study drug.
- The administration and/or use of an expired study drug.

Note: Cases of participants missing doses of the study drug are not considered reportable as medication errors.

11.9.15. Patient-reported Outcome Measures

During the screening period, the participant should complete 14 consecutive days of questionnaires on an electronic device as outlined in Table 4. In order to meet study entry criteria, the participant must complete at least 4 baseline assessments (each) of BPI Worst Pain and Worst Stiffness NRS items, at least one baseline PROMIS assessment, and one baseline 5-level EQ-5D (EQ-5D-5L) assessment. The patient should be encouraged to complete all 14 consecutive days of screening questionnaires to ensure robust baseline data collection for the study PRO endpoints.

11.9.15.1. PROMIS-Physical Function Questions

Physical function will be assessed using 15 questions from the PROMIS-Physical Function (PROMIS-PF) item bank that was developed by the National Institutes of Health. The PROMIS-PF questions will include 2 scales to measure tumor location-specific physical function. The first scale includes 13 questions and is intended for use by participants with lower-extremity tumors (eg, knee). The second scale includes 11 questions and is intended for use by participants with upper-extremity tumors (eg, digits). Nine of the PROMIS-PF questions are overlapping (ie, included in both lower- and upper-extremity scales). The 15 questions use one of two 5-point verbal rating scales: either 1="unable to do", 2="with much difficulty", 3="with some difficulty", 4="with a little difficulty", and 5="mot at all."

11.9.15.2. Worst Stiffness Numeric Rating Scale

The Worst Stiffness NRS is a single question that asks the participant to assess their worst stiffness in the last 24 hours. Participants rate their worst stiffness on a scale of 0 to 10, where 0 is "no stiffness" and 10 is "worst imaginable."

11.9.15.3. Brief Pain Inventory-Short Form

The Brief Pain Inventory-Short Form (BPI-SF) was developed with support from the NCI and the World Health Organization (WHO). It is a 9-item questionnaire that assesses the severity and impact of pain, across several dimensions. Two questions of the BPI-SF, the worst pain question, which measures pain severity at its worst in the last 24 hours, and the average pain question, which measures average pain, will be used in this study. For both questions, participants rate their pain on a scale of 0 to 10, where 0 is "no pain" and 10 is "pain as bad as you can imagine."

11.9.15.4. EQ-5D-5L

The EQ-5D-5L was developed by the EuroQol Group. The measure assesses 5 areas of functioning and consists of the EQ-5D descriptive system and the EQ Visual Analogue Scale. Answers to the descriptive questions are given by selecting among 5 levels of difficulty, while the Visual Analogue Scale is scored from 0 to 100.

11.9.15.5. GP5 from FACT-G

The GP5 "burden-of-side-effects" question is an item taken from the Functional Assessment of Chronic Illness Therapy (FACIT) FACT-G questionnaire, a validated measure that has been used extensively in clinical studies (FACIT, 2020). It asks participants to indicate how bothered they are by side effects of study treatment on a scale of 0 to 4, where 0 is "Not at all" and 4 is "Very much."

11.9.15.6. Patient Global Impression of Change

Three PGIC questions will be asked of participants. These questions assess the participant's impression of change to the following, since the start of the study: their symptoms at the site of their tumor, ROM at the site of their tumor, and tumor-related physical functioning.

For all 3 questions, participants answer on a scale of 1 to 7, where 1 is "Very Much Improved", 2 is "Much Improved", 3 is "Minimally Improved", 4 is "No Change", 5 is "Minimally Worse", 6 is "Much Worse" and 7 is "Very Much Worse."

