7. INVESTIGATIONAL PLAN

7.1. Overall Study Design

This is a multicenter, randomized, placebo-controlled study of vimseltinib in patients with TGCT, consisting of 2 parts: Part 1 is double-blinded and Part 2 is open label. Symptomatic patients with histologically confirmed TGCT for whom surgical resection will potentially cause worsening functional limitation or severe morbidity will be eligible. Patients who received anti-CSF1/CSF1R therapy previously (except for imatinib or nilotinib) will be excluded. The study will evaluate efficacy, safety, clinical outcome assessments, PK, and pharmacodynamics of vimseltinib in this population.

The study will consist of a 42-day screening period prior to the first dose of study drug, a Part 1 double-blinded treatment period of 24 weeks (referred to in 28-day cycles) and a Part 2 open-label period until Week 49 (Figure 1). Participants will continue treatment after Week 49 during the extension period. There will also be an End-of-Treatment (EOT) Visit within 7 days after the decision to stop study drug, a Safety Follow-up Visit 30 days (\pm 5 days) after the last dose of study drug, and a Disease Follow-up period of up to 2 years or until initiation of new TGCT treatment or surgery, whichever occurs first. A summary of visit flow is provided in Figure 2. Participants will be allowed to undergo surgical resection only after completion of Part 1.

Approximately 120 participants will be randomized in a 2:1 ratio to receive either vimseltinib at the dose of 30 mg twice weekly (biw) (n=80) or placebo (n=40) for 24 weeks. Randomization will be stratified for tumor location (lower limb/all other) and region (U.S./non-U.S.).

At Week 25, the primary and secondary endpoints will be assessed, and participants randomized to placebo in Part 1 will have the option to crossover and receive open-label vimseltinib in Part 2 upon completion of Part 1. Participants randomized to placebo in Part 1 with confirmed disease progression by blinded IRR before Week 25 are eligible for early entry into Part 2. Participants randomized to vimseltinib in Part 1 with confirmed disease progression by IRR before Week 25 will discontinue from study, while those without confirmed disease progression by IRR before Week 25 will continue to receive vimseltinib in Part 2 upon completion of Part 1.

[figure not shown]

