11.9.16. Clinician Reported Outcome Measures

11.9.16.1. Clinician Global Impression of Change

Three CGIC questions will be asked of clinicians. These questions assess the clinician impression of change in the participant's symptoms, ROM, and physical function, since the start of the study.

The CGIC questions use the same scale as the PGIC.

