8.1. Baseline

For all evaluations unless otherwise noted, baseline is defined as the most recent non-missing measurement prior to the first administration of study drug.

For the PROs collected multiple times during the screening period such as the Brief Pain Inventory (BPI) Numeric Rating Scale (NRS) for worst pain and average pain, and the NRS for worst stiffness, baseline will be the average of measurements taken during the period prior to Cycle 1 Day 1 which are the 14 days of assessments closest to and prior to Cycle 1 Day 1. A

participant must have at least 4 assessments available to compute this average, otherwise it is set to missing. For crossover participants and data from Part 2, baseline is defined to most recent measurement prior to first administration of vimseltinib. For BPI and NRS, the crossover baseline is defined as the average of Weeks 2 and 3 of Cycle 6 in Part 1.

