9.10.7. Exploratory Efficacy Analysis (Part 1 & 2)

There will be no formal testing for exploratory endpoints, descriptive statistics will be presented and nominal p-values may be provided.

As will be done for safety analyses, exploratory efficacy endpoints presented over time will be summarized following two different approaches. The first approach will be limited to data from Part 1 and will focus on comparisons between participants who received vimseltinib versus participants who received placebo during this period. The second approach will combine data from both Part 1 and Part 2 (including extension period) and will focus on the observations and assessments while participants are receiving vimseltinib. Therefore, in this second approach, participants randomized to Placebo in Part 1, will have as their reference day the first dose date of vimseltinib which will occur in Part 2, and their data from Part 1 while receiving placebo will be excluded.

For observed value and change from baseline analyses, summary statistics at each scheduled visit will be presented.

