9.10.7.6. Clinician and Patient Global Impression of Change and Severity

Clinician Global Impression of Change (CGIC) and of Severity (CGIS) as well as Patient Global Impression of Change (PGIC) and of Severity (PGIS) will be summarized over time, including Week 13, Week 25 and Week 49 as timepoints of interest.

- Observed value will be summarized for CGIC and PGIC, as well as response in CGIC and PGIC, defined as an answer of "Very Much Improved" or "Much Improved"
- Observed value and change from baseline will be summarized for CGIS and PGIS.

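### In the exploratory on-vimseltinib summaries, crossover participants' PGIC/CGIC answers still span their placebo period, and those who cross over early have no defined pain or stiffness baseline

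*Protocol*

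**What the plan says.** **Re-basing.** SAP 9.10.7 summarizes exploratory efficacy endpoints over time in two ways. The first uses Part 1 only. The second joins Part 1 and Part 2 and looks at time on vimseltinib. In it, placebo participants "will have as their reference day the first dose date of vimseltinib which will occur in Part 2", and their placebo-period data are left out.

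**PGIC and CGIC.** Protocol 11.9.15.6 says of the PGIC: "These questions assess the participant's impression of change to the following, since the start of the study". Protocol 11.9.16.1 says the CGIC covers "change in the participant's symptoms, ROM, and physical function, since the start of the study". Both continue after crossover (Protocol Tables 2 and 5). SAP 9.10.7.6 summarizes the observed answers and the share in the top two improvement categories, with Weeks 13, 25 and 49 of interest. It makes no adjustment for crossovers.

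**Pain and stiffness baseline.** SAP 8.1 gives a general crossover baseline, the last value before vimseltinib starts, and then a specific one: "For BPI and NRS, the crossover baseline is defined as the average of Weeks 2 and 3 of Cycle 6 in Part 1". No alternative is given for a participant who lacks those weeks.

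**Early crossover.** Protocol 7.1 states that placebo participants with "confirmed disease progression by blinded IRR before Week 25 are eligible for early entry into Part 2". Sections 10.5 and 11.5.1 describe the same route.

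**The concern.** These are two separate defects in the same set of summaries.

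1. Removing placebo-period records does not remove placebo-period change from a later answer that looks back to study entry. Someone already much improved on placebo who then stays level is counted as a responder on vimseltinib. Someone who worsened on placebo and then recovered may report no change. The summary is presented as vimseltinib experience but does not isolate it.

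2. A placebo participant who enters Part 2 before enough Cycle 6 readings exist has no baseline under the written rule. Later change from baseline in BPI worst pain, BPI average pain and worst stiffness is then undefined for that person. The gap is selective, because early entry requires progression on placebo.

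At stake are the Protocol 6.1 exploratory objectives on long-term efficacy and symptomatic relief.

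**Working it through.** **The plan's own figure.** The documents give no number on this point. Their only sample-size figure, 98% power for response rates of 35% vs 5% with 80 and 40 participants, reproduces by exact enumeration of the two-sided Fisher test at 98.3%. Nothing below affects it.

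**Step 1: time covered by a PGIC/CGIC answer.** Protocol Table 2 puts crossover Cycle 1 Day 1 at study Week 25 and crossover Cycle 7 Day 1 at study Week 49. Weeks since study start = study week - 1, and weeks on placebo = 25 - 1 = 24.

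| Weeks on vimseltinib | Study week | Weeks covered | Placebo share |
|---|---|---|---|
| 12 (re-based Week 13) | 37 | 36 | 24/36 = 67% |
| 24 (re-based Week 25) | 49 | 48 | 24/48 = 50% |
| 48 (re-based Week 49) | 73 | 72 | 24/72 = 33% |

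**Step 2: effect on a pooled responder rate.** Let m be the number of crossovers, d the shift in their responder rate caused by the longer look-back, and 80 the number randomized to vimseltinib. Shift in pooled rate = m × d / (80 + m). The documents give no PGIC or CGIC rates, so d is assumed.

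| m | Crossover share | d = -10 | d = +5 | d = +10 | d = +20 |
|---|---|---|---|---|---|
| 30 | 30/110 = 27% | -2.7 | +1.4 | +2.7 | +5.5 |
| 34 (40 less 15% dropout) | 34/114 = 30% | -3.0 | +1.5 | +3.0 | +6.0 |
| 40 | 40/120 = 33% | -3.3 | +1.7 | +3.3 | +6.7 |

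All shifts are in percentage points. If crossovers are shown in their own column, that column carries the whole of d.

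**Step 3: who lacks a pain or stiffness baseline.** The only scheduled on-treatment MRI before Week 25 is at Cycle 4 Day 1 (Protocol Table 1). Progression confirmed from that scan can lead to crossover before Cycle 6. The number is not stated. If 2.5% to 15% of the 40 placebo participants cross over that early, 40 × 0.025 = 1 to 40 × 0.15 = 6 are affected.

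**Step 4: can an earlier cycle serve?** In Weeks 2 and 3 of each of Cycles 2 to 6, Protocol Table 4 schedules BPI on all 14 days and stiffness on 7. The SAP's minimum for such averages is 4. A participant who progresses at Cycle 4 Day 1 should therefore have a usable Cycle 3 average.

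**The case against.** **These analyses are exploratory and untested.** This stands. SAP 9.10.7 rules out formal testing, and SAP 9.10.3 limits the secondary comparisons to Part 1, apart from duration of response. A reader might infer that the key secondary stiffness or BPI-30 results are affected; they are not.

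**Pooling of the arms is inferred.** This stands in part. SAP 9.1 presents data by treatment group and overall by default, Protocol 12.4.10 has PGIC and CGIC summarized by treatment group, and for duration of response SAP 9.10.4.3 says expressly when groups are combined. Separate columns would protect the randomized vimseltinib column. They would not cure the crossover column, whose re-based Week 25 answer still includes 24 placebo weeks.

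**PGIS and CGIS avoid the problem.** This is correct. They ask about the present, so change from a re-based baseline is sound. They cover range of motion and physical function but do not correct the PGIC/CGIC responder rates.

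**The item wording is not in the documents.** This stands. The point rests on the Protocol's description of the questions.

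**Stronger readings the documents do not support.**
- A reader might infer that the Cycle 6 baseline also credits placebo change to vimseltinib. For on-time crossovers it does the reverse and removes that change.
- A reader might infer that everyone who progressed on placebo, or every early entrant, is lost. Progression found on the Week 25 MRI, or confirmed after Cycle 6 Week 3, leaves the Cycle 6 weeks available. Observed values are still summarized for all (SAP 9.10.7.7 and 9.10.7.9).
- A reader might take an assumed 10% to 30% improving on placebo, 4 to 12 of 40, and add 4/120 = 3.3 to 12/120 = 10 points to the pooled rate. That is a one-directional ceiling: it supposes that all 40 cross over and that none of these people would have responded on vimseltinib. At an assumed 50% response it halves to 1.7 to 5 points, and worsening on placebo would act in the opposite direction.

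**Conclusion.** Both defects follow from the stated rules, and both are confined to the exploratory summaries that combine Part 1 and Part 2.

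1. For PGIC and CGIC, the re-basing does not deliver the exclusion of placebo experience that the SAP describes. The placebo share of the period covered is certain for Week 25 crossovers, given the Protocol's description of the items. The direction and size of the bias are not known; the -3.3 to +6.7 point range rests wholly on assumed shifts and on up to 40 crossovers.

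2. For BPI and worst stiffness, change from baseline is undefined for placebo participants who cross over before enough Cycle 6 Week 2 and 3 readings exist. The number is probably small, since Protocol 7.2 calls the disease slowly progressing. The loss is selective.

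The matter is modest in weight but worth correcting, since the summaries serve stated objectives and the repair uses data already collected.

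**What to change.** **SAP 9.10.7.6.** In the approach that combines Part 1 and Part 2, do not pool crossovers with participants randomized to vimseltinib for PGIC and CGIC. Report by original arm and label the crossover column as change since study start. Add a descriptive shift table for crossovers from the End of Part 1 answer to later answers. Do not add a new responder rule: requiring a better category than at End of Part 1 would make anyone already in the top category an automatic non-responder. The sponsor should first check the exact item wording used after crossover.

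**SAP 8.1.** Keep Weeks 2 and 3 of Cycle 6 for participants who complete Part 1. For those who cross over earlier, use the average of Weeks 2 and 3 of the last Part 1 cycle with at least 4 readings before the first vimseltinib dose.

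**Cost.** Two SAP wording changes and one table. No new data and no protocol amendment are needed, and sample size, power and alpha do not change.
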